Efficacy of Extracorporeal Shock Wave Therapy On Cervical Myofascial Pain Following

Neck Dissection Surgery

12-2-2020

Study Protocol

Objective: Cervical myofascial pain is one of the problems that contribute in chronic neck pain

following neck dissection surgery, so we aimed to investigate efficacy of extracorporeal shock

wave therapy (ESWT) on cervical myofascial pain in expression of decreasing pain and improving

cervical range of motion (ROM).

Design: This trial is a single blind randomized control experimental study.

Subjects: 46 patients with cervical myofascial pain following neck dissection surgery were

recruited in this trial and subdivided at random into two equal groups. ESWT Group: received

ESWT once a week for 4 weeks (0.25 ml/mm², 1000 shocks) plus topical none steroidal anti-

inflammatory drug (NSAID; 3 times /day for 4 weeks). Control Group: received only topical

NSAID.

Outcome measures: Pain assessment was measured by visual analogue scale (VAS) and pressure

algometry. Cervical range of motion device (CROM) was used for assessment of lateral flexion

and rotation of neck ROM for both sides. All measurements were collected before the beginning

of the study, after 2 weeks and at the trial termination (after 4 weeks).

Results: ESWT Group revealed significant improvement in all parameters at post I and II compared to control group (p < 0.001), while the control group revealed only a statistical decrease in VAS at post I without any statistical difference in pain threshold and neck ROM, however, there were statistical differences in all parameters at post II compared to pre-treatment and post I (p < 0.001).

Conclusion: Higher statistical results were achieved with ESWT without any side effects confirming the safety and efficiency of ESWT in cervical myofascial pain.

Subject characteristics:

The mean \pm SD of subjects' characteristics of both groups is illustrated in Table 1. There weren't statistical differences (p>0.05) in the mean of age, weight, height and sex distribution between groups.

Effect of treatment on rotation and side bending ROM, VAS and PTT:

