Mixed MANOVA showed a significant interaction effect of treatment and time (Wilks' Lambda = 0.01, F (12, 30) = 227.55, p = 0.001, = 0.98). There was a significant main effect of time (Wilks' Lambda = 0.005, F (12, 30) = 489.27, p = 0.001, = 0.99). There was a significant main effect of treatment (Wilks' Lambda = 0.03, F (6, 36) = 162.55, p = 0.001, = 0.96). Table 2 and 3 showed descriptive statistics of rotation and side bending ROM, VAS and PTT and the statistical level of

comparison between groups as well as significant level of comparison between pre, post I and post II in each group.

Between group comparisons

Pre-trial evaluations revealed non statistical difference between both study and control groups in all measured variables (p > 0.05). A significant increment of neck rotation, and side bending ROM in both directions away and toward the operated side with a marked improvement of PPT was reported at post I and II in the study group compared to control group (p > 0.001). Moreover, there was a significant decrease in VAS of the study group at post I and at post II compared to control group (p > 0.001).

Within group comparison

Statistical improvements were reported in the rotation and side bending ROM in both directions away and toward the operated side and also in PPT in the study group at post II in comparison with pre-treatment and post I (p < 0.001); furthermore, a significant amelioration in the rotation and side bending ROM in both directions and PPT at post I compared with that pre-treatment (p < 0.001). There was a statistical diminution of VAS in the study group at post II compared to pre-treatment and post I (p < 0.001); and also, in VAS at post I in comparison with pre-treatment (p < 0.001).

There was no statistical difference in the rotation and side bending ROM in both directions and in PPT between pre-treatment and post I (p > 0.05) in the control group; However there was a statistical increase in the rotation and side bending ROM in both directions and also in PPT at post II in comparison with pre-treatment and post I (p < 0.001). There was a statistical decrease in VAS in the control group at post II compared with that at pre-treatment and post I (p < 0.001); as well in VAS at post I in comparison with pre-treatment (p < 0.001).

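### The treatment main effect in the mixed MANOVA averages the pre-treatment visit with the two post-treatment visits, so it is a diluted measure of the treatment effect

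*Combined protocol and SAP*

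**What the plan says.** The Subjects paragraph of the protocol has "46 patients with cervical myofascial pain following neck dissection surgery were" recruited and "subdivided at random into two equal groups". The Outcome measures paragraph sets three measurement times: "All measurements were collected before the beginning" "of the study, after 2 weeks and at the trial termination (after 4 weeks". The later text calls these pre, post I and post II.

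The mixed MANOVA paragraph, under the heading on the effect of treatment on ROM, VAS and PTT, reports three omnibus terms:

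- a treatment-by-time interaction, F (12, 30) = 227.55;
- a time effect: "There was a significant main effect of time (Wilks' Lambda = 0.005, F (12, 30) = 489.27, p = 0.001";
- a treatment effect: "There was a significant main effect of treatment", with Λ = 0.03, F (6, 36) = 162.55 and an effect size of 0.96.

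Under Between group comparisons, the document says of the first visit: "Pre-trial evaluations revealed non statistical difference between both study and control groups in all measured variables". It then reports differences between the arms at post I and at post II separately.

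**The concern.** In a mixed MANOVA, the between-subject term compares the arms on the equally weighted mean of every level of the time factor. If the pre-treatment visit is one of those levels, a third of the contrast comes from a visit at which treatment cannot have had an effect. The result mixes the post-treatment differences with an expected zero and with whatever baseline imbalance chance produced.

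This F and the 0.96 stand among the efficacy results, so a reader may take them as the overall strength of evidence for ESWT. They answer a different question from the one the trial asks. The significant interaction makes the average harder still to interpret, because it says that the difference between arms changes across the visits being averaged.

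The issue is which contrast the overall test addresses.

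**Working it through.** **Inputs from the document.** There are six outcomes: rotation in two directions, side bending in two directions, VAS and pressure pain threshold. There are three visits. The F values and degrees of freedom are those of the mixed MANOVA paragraph.

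**1. Reproduce the printed figure.** With two groups, Λ = 1/(1 + F × df1/df2).

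- Treatment: 162.55 × 6/36 = 27.09, so Λ = 1/28.09 = 0.0356 and 1 − Λ = 0.964. The printed 0.96 is therefore 1 − Λ. The printed Λ of 0.03 agrees by truncation.
- Time: 489.27 × 12/30 = 195.71, so Λ = 0.0051.
- Interaction: 227.55 × 12/30 = 91.02, so Λ = 0.0109.

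**2. Is the pre-treatment visit a time level?** The numerator df for time is 6 × (T − 1), where T is the number of levels. T = 3 gives 12, as printed. The two post-treatment visits alone would give 6. Only three measurement times exist, so the pre-treatment visit is one of the levels.

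**3. What the treatment term estimates.** Write d_pre, d_I and d_II for the differences between arms at the three visits. The contrast is (d_pre + d_I + d_II)/3. Under randomisation d_pre has expectation 0, which leaves (d_I + d_II)/3.

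- Against the post-treatment mean (d_I + d_II)/2, the ratio is 2/3 whatever d_I and d_II are.
- Against the week-4 difference d_II, it is 67% if d_I = d_II, 50% if d_I = d_II/2, and 42% if d_I = d_II/4.

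**4. Efficiency for one outcome.** Assumptions, not given in the document: SD of 1 at every visit and a common between-visit correlation r. The SD of the three-visit mean is √((1+2r)/3), and that of the two-visit mean is √((1+r)/2). The ratio of standardised effects is (2/3) × √((1+r)/2) / √((1+2r)/3). Its square is the relative efficiency.

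| r | SD, 3 visits | SD, 2 visits | Ratio | Efficiency |
|---|---|---|---|---|
| 0.3 | 0.730 | 0.806 | 0.736 | 54% |
| 0.5 | 0.816 | 0.866 | 0.707 | 50% |
| 0.7 | 0.894 | 0.922 | 0.687 | 47% |

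**5. Power, as an illustration.** Assumptions: one outcome, 23 per arm, two-sided 0.05, a difference of 0.8 SD at both post-treatment visits, r = 0.5. Power is 60% for the three-visit mean, 88% for the post-visit mean, and 97% for the post-visit mean adjusted for baseline, whose SD is √((1+r)/2 − r²) = 0.707. Over r = 0.3 to 0.7 the three figures run 70–53%, 92–84% and 95–99.5%.

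**6. Baseline gap.** Given an observed gap b, and under the same assumptions, the expected chance difference at each post-treatment visit is rb. The three-visit mean then carries (b + rb + rb)/3 = (1+2r)b/3, which is 0.53b, 0.67b and 0.80b at r = 0.3, 0.5 and 0.7. An unadjusted post-only mean carries rb, which is 0.3b, 0.5b and 0.7b. Adjustment for the pre-treatment value removes this term.

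**7. What cannot be computed.** The text available gives no means, SDs or correlations, so the F that the trial would obtain from the post-treatment contrast is unknown.

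**The case against.** The strongest reply is that nothing depends on this term. The interaction, which tests differential change, is reported first. The differences between arms at each post-treatment visit follow. The efficacy statement in the Results paragraph is about post I and post II and does not cite the main effect. Listing all three omnibus terms is routine output, and main effect is simply the standard name for the between-group term. All of this stands, and it limits the consequence.

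Four stronger readings that a reader might infer are not supported:

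- **The reported significance is false.** Under randomisation the test remains valid against no effect at any visit, and the expected distortion is towards dilution. It rejected anyway, so lost power did not change its result.
- **The 0.96 is understated by a third.** That figure is 1 − Λ, a multivariate proportion bounded at 1. The two-thirds factor applies to a mean difference and does not carry over to it.
- **The efficiency figures describe the reported test.** They are for one outcome under assumed correlations. The six-outcome Wilks test also depends on covariances between outcomes, which are not given.
- **A baseline gap b adds only b/3.** That omits carry-over into the later visits (step 6).

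It is also fair to say that a post I/post II average need not describe either visit, and that a post-only test without adjustment would still carry rb. The first is a reason to keep the visit-specific results beside it. The second is a reason to adjust for baseline. A cautionary sentence alone would correct the interpretation, but it would leave the paper without an overall test of the contrast of interest.

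**Conclusion.** The point holds for this omnibus figure. F (6, 36) = 162.55 and 0.96 refer to the average over pre, post I and post II. That follows from the stated visits and the printed degrees of freedom and needs no assumption. In expectation the contrast is two thirds of the mean post-treatment difference, which needs only randomisation. The loss of efficiency to about half (54% to 47%) and the carried gap of (1+2r)b/3 rest on equal SDs and a common r, taken as 0.3 to 0.7.

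The test is diluted, not invalid. A reader might infer that the efficacy conclusion falls with it. The document does not support that, because the conclusion also rests on the interaction and the visit-specific comparisons. The change is worth making because the pre-treatment values are already collected and would give a more precise and more relevant overall test.

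**What to change.** Do not present the three-visit treatment main effect as evidence of a treatment effect. Report instead the overall between-arm test on post I and post II, with the six pre-treatment values as covariates. Keep the treatment-by-time interaction as the test of differential change, and keep the visit-specific comparisons. Replace F (6, 36) = 162.55 and 0.96 with the new result, and say in one sentence which visits it covers.

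The cost is one re-run on existing data, with no added patients or visits. The reported F and effect size will change. The covariates use six error degrees of freedom: for a test on the post I/post II mean of the six outcomes, df2 falls from 36 to 30.

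When re-running, state the number analysed. The printed error df imply 36 + 2 + 6 − 1 = 43 and 30 + 2 + 12 − 1 = 43 patients, against 46 recruited. With 46 the terms would be F (6, 39) and F (12, 33). This is a separate matter and does not affect the point above, but the new test should not repeat the gap without explanation.
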